6.5 Minimizing Potential Bias

To address potential effects of an unblinded trial design on outcome determination, we have chosen an objective primary endpoint (HF hospitalization or CV death) and will use a blinded Clinical Endpoints Committee (CEC) to classify potential endpoints. Source data (i.e., history, laboratory procedures and discharge summaries) on all deaths and hospitalizations will be reviewed by the CEC in a consistent, standardized and unbiased manner. Final cause for each event will be adjudicated using definitions that will be established in the CEC Charter.

Another potential source of bias relates to the possibility that the greater frequency of medical visits due to natriuretic peptide guidance will lead to improved patient outcomes through a mechanism other than

biomarker-guided titration of HF therapy. While GUIDE-IT will mandate frequent visits in the usual-care group (as consistent with standard practice), any observed differential in the number of medical interventions (driven by out-of-range natriuretic peptide levels in apparently stable patients) may be the mechanism by which any treatment effects are realized. The alternative of mandating extra clinical visits for the usual-care arm to mirror the visit pattern of the biomarker-guided arm carries risk of biasing the trial results. Those extra visits, which would not occur in regular clinical practice, could lead to extra testing and treatment modifications that result in the outcomes of the two arms converging, thus masking a real treatment benefit. While there is no perfect solution to this problem, we will have detailed data on the content of each clinic visit in both treatment arms; thus, we will determine how often these visits included significant modifications of medical therapy.

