6.8 Economic Data Collection Procedures

Total medical costs can be divided into five major components: inpatient hospital care, inpatient physician care, outpatient (ED visits, observational stays, rehabilitation stays, nursing home stays) physician care,

outpatient testing, and outpatient medications. Hospital costs will be calculated using hospital billing data, with charges converted to costs using the departmental charge-to-cost conversion factors available from each hospital's annual Medicare Cost Report. Physician costs (both inpatient and outpatient) will be estimated by mapping major procedures and physician services recorded on the case report form and hospital bills to appropriate current procedural terminology (CPT) codes in the Medicare Fee Schedule. Outpatient medication costs will be based on the *Drug Topics Red Book* average wholesale price, discounted as appropriate to reflect market acquisition costs. Outpatient testing costs will be assigned using the Medicare Fee Schedule for the physician component and the Medicare ambulatory payment classification (as per rates for the institutional and laboratory component).

Hospital bills for patients in the U.S. (detailed, summary ledger, and UB-04) will be collected by the GUIDE-IT EQOL CC staff after discharge from the hospital This process typically starts with a call to the head or the representative of the given hospital's patient accounting department to request the bill, and is followed by a written letter including a copy of the signed consent form if requested. Once received, in order to maintain confidentiality, the patient's name will be removed and replaced with the GUIDE-IT patient study number and patient initials before further processing.

In addition, cost-to-charge ratios (Medicare Cost Report Worksheets C and D-1, Part 2) will be obtained for each hospital where a GUIDE-IT hospitalization is reported. These reports can be obtained from the hospital in question, the Medicare Intermediary for that region, or the Centers for Medicare and Medicaid Services. Reports will be obtained for each year of study enrollment and follow-up up to the most recent report available at the start of the data analysis phase.

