To estimate the incremental cost effectiveness of the biomarker-guided approach relative to usual care, we will calculate a base case cost-effectiveness ratio that defines the incremental cost required to add an extra life year with the biomarker-guided strategy relative to usual care. A second series of analyses will calculate the corresponding cost-utility ratio, using utility data from the EQ-5D collected in the GUIDE-IT trial. These analyses will use the societal perspective and a lifetime time horizon so that the estimated incremental cost-effectiveness and cost-utility ratios can be compared with societal benchmarks. Where extrapolations from empirical data and other assumptions are required, they will be based, to the extent possible, on the empirical data from the GUIDE-IT trial and will be accompanied by appropriate examination of the effects of uncertainty using both stochastic methods and sensitivity analyses. For descriptive purposes, we will also calculate within-trial cost-effectiveness and cost-utility ratios, since they do not require any extrapolations. However, these within-trial ratios are limited due to their failure to account fully for long-term benefits and costs, and the absence of comparative benchmarks. At the time of analysis, costs will be adjusted to the most recent year for which the Producer Price Index has been published. Both costs and life expectancy will be discounted to present value at a 3% annual discount rate (with rates from 0 to 7% examined in sensitivity analyses).

Since many of the patients will remain alive at the conclusion of the trial, a method is required for converting observed trial experience into the corresponding lifetime survival and cost figures needed for use in the incremental cost-effectiveness calculations. There are three general methods that we have previously used to make the necessary lifetime extrapolations called for in cost-effectiveness analysis: use of the trial data for extrapolation, use of secondary data sources to base the extrapolations upon, and use of Markov models. GUIDE-IT will provide a rich empirical data set involving up to 2 years of clinical outcome, cost, and utility data, with over 2,000 patient-years of follow-up information. We will use these data in age-based survival models to create estimates for each GUIDE-IT patient of life expectancy, quality-adjusted life expectancy and lifetime medical costs.

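### The cost-effectiveness ratios are declared societal, but every cost the protocol defines, collects or extrapolates is medical

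*Protocol*

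**What the plan says.** Section 8.13 of the protocol plans a base-case ratio (incremental cost per added life year) and a cost-utility ratio using EQ-5D utilities. It fixes the viewpoint for both: "These analyses will use the societal perspective and a lifetime time horizon". The reason follows at once: "so that the estimated incremental cost-effectiveness and cost-utility ratios can be compared with societal benchmarks".

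Section 6.8 is the only place that says what counts as cost. It begins: "Total medical costs can be divided into five major components". The five are hospital inpatient care, inpatient physician care, outpatient physician care, outpatient tests and outpatient drugs. The sources are bills and fee schedules:

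- Hospital care: "Hospital costs will be calculated using hospital billing data". For US patients the bills "will be collected by the GUIDE-IT EQOL CC staff after discharge from the hospital".
- Physician care: "Physician costs (both inpatient and outpatient) will be estimated by mapping major procedures and physician services" to procedure codes priced by the Medicare Fee Schedule.
- Tests: Medicare rates for the physician part and for the institutional and laboratory part.
- Drugs: a discounted wholesale price.

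Elsewhere, 8.13 adds a descriptive count of health care items (hospital days, cardiac procedures, physician and emergency visits). Its lifetime extrapolation predicts survival, quality-adjusted survival and medical costs for each patient. Appendix A has one economic row, for medical resource use and cost.

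**The concern.** The perspective of an economic evaluation determines which costs enter the numerator of the ratio. A societal numerator includes resources outside the health care sector, such as patient and caregiver time, informal care, travel and lost production. The protocol claims that perspective and gives a purpose for it, but its costing rules supply only the medical part.

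Resource use, cost and cost effectiveness form a listed secondary endpoint (sections 1.2 and 7.2). If the plan is followed to the letter, the trial would publish a ratio labelled societal and judge it against societal benchmarks, although the numerator stops at medical care. Readers could not repair this from the publication, because the missing items would never have been collected.

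**Working it through.** **1. The plan's own cost figure.** The only numerical statement about cost precision in 8.13 is a 95% confidence half-width of 1,208 USD (about 0.12 SD). It assumes a mean of 10,000 USD per arm, a coefficient of variation of 1 (so SD = 10,000 USD) and more than 500 patients per arm with cost data.

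Half-width = 1.96 × SD × √(2/n):

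- n = 500: 1.96 × 10,000 × √(2/500) = 1,239.6 USD (0.124 SD)
- n = 526: 1.96 × 10,000 × √(2/526) = 1,208.6 USD (0.121 SD)
- n = 550: 1.96 × 10,000 × √(2/550) = 1,181.9 USD (0.118 SD)

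The stated figure reproduces at about 526 per arm, which fits the stated minimum. There is no arithmetic error; the problem is one of definition.

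**2. Declared perspective against specified costs.**

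| Element | Where | Scope |
|---|---|---|
| Perspective of both ratios | 8.13 | Societal |
| Purpose of that choice | 8.13 | Comparison with societal benchmarks |
| Definition of total cost | 6.8 | Medical, five components |
| Valuation sources | 6.8 | Hospital bills, Medicare schedules, drug price list |
| Extra resource counts | 8.13 | Health care items, descriptive |
| Quantity extrapolated to lifetime | 8.13 | Medical costs |
| Scheduled economic data | Appendix A | Medical resource use and cost |

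The first two rows require a societal numerator. Each of the other five supplies a medical one, and no section collects or prices a cost outside medical care. The ratio as specified is therefore a health-care-sector ratio.

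**3. Size.** The effect on the ratio cannot be computed, because the protocol gives no quantity or unit cost for any omitted item. As an assumption only, suppose the omitted costs differ between arms by D USD per patient. The incremental cost then shifts by D:

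- D = 500: 500 / 1,208 = 0.41 half-widths
- D = 1,000: 1,000 / 1,208 = 0.83 half-widths
- D = 2,000: 2,000 / 1,208 = 1.66 half-widths

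These values show scale, not likelihood. The sign of D is unknown. The yardstick comes from an illustrative 10,000 USD mean, while the base-case ratio is a lifetime quantity.

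**4. Facility costs inside the medical total (secondary).** Section 6.8 names its third component as "outpatient (ED visits, observational stays, rehabilitation stays, nursing home stays) physician care". It states how to price physician services, hospital bills, tests and drugs. It states no rule for the facility cost of a rehabilitation or nursing-home stay. The resource items named in 8.13 do not include days of such stays.

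**The case against.** **Detail belongs elsewhere.** Section 9.2 refers detail on economic data collection to the Manual of Operations, and 8.13 says that only the general plan of the cost-effectiveness work can be fixed in advance. That is a fair answer for individual prices, and it is why the facility-cost question is secondary. It does not answer the main point. The perspective is part of the general plan, the protocol fixes it explicitly, and the protocol's own scope of cost does not match it.

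**Little is at stake.** Cost is one of eight secondary items, and the primary analysis, its power and safety are untouched. That is correct and limits the weight of the point.

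A reader might infer three stronger things, which the documents do not support.

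- *Emergency and observation stays are costed as physician care only.* The parenthesis in 6.8 follows the word outpatient and can be read as defining the setting. The hospital-billing rule is not limited in its wording to inpatient stays and may capture such charges. Tests carry an institutional component.
- *The omission favours the guided arm.* Section 6.5 does raise "the greater frequency of medical visits due to natriuretic peptide guidance" as a possible source of bias, and extra contacts cost patients time. But 6.3.2 sets one visit schedule for both arms. The two-week reassessment in 6.3.3 follows a therapy change in either arm and may be a remote laboratory check. Hospital stays also consume patient and caregiver time; if the strategy works, more of that burden falls on usual care. The net direction is unknown.
- *Total cost is short by 6% to 9%.* This needs an assumed 30-day stay at 200 to 300 USD per day (6,000 to 9,000 USD) in 10% of patients, or 600 to 900 USD against a 10,000 USD mean. That is a level of cost, whereas the ratio uses a difference between arms. With equal stay rates the error in the difference is zero. If the design's 20% relative reduction (8.1) carried over to stays, from 10% to 8%, it would be 0.02 × 6,000 to 9,000 = 120 to 180 USD. Every input except the 20% and the 10,000 USD example is assumed.

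**Conclusion.** The point holds as an internal contradiction. Section 8.13 declares a societal perspective for both ratios, while 6.8, the rest of 8.13 and Appendix A provide for medical costs only. As specified, the ratios take a health-care-sector view and would be mislabelled, and the comparison with societal benchmarks would not be like with like. This conclusion rests on the text alone and needs no assumed price. Neither the size nor the direction of the error can be derived from the protocol.

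The correction should be made because it changes what the trial may claim on a listed secondary endpoint and costs little. The missing facility-cost rule for rehabilitation and nursing-home stays is a separate, smaller gap, and the main conclusion does not depend on it.

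**What to change.** **Preferred.** In 8.13, name the perspective as health-care sector and tie it to the cost definition in 6.8. Possible wording: *The base-case ratios take a health-care-sector view, counting medical costs as defined in section 6.8, over a lifetime horizon. They will be compared only with benchmarks suited to that view.* This is a wording change and needs no new patient data. The price is a narrower claim.

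**Alternative.** Keep the societal label and add the non-medical items to 6.8 (for example patient and caregiver time, travel and lost work), with the source and unit value of each. This preserves the aim stated in 8.13 but needs extra data collection in both arms.

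**Secondary, under either choice.** Confirm that days of rehabilitation and nursing-home stay are captured, and state in 6.8 or the Manual of Operations how their facility cost is priced. If the days are already recorded, this is a short addition to the costing rules. If not, it needs an added data field, since the items listed in 8.13 do not show them.

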8.14 Data Safety Monitoring Board and Interim Analyses

For ethical reasons, an interim examination of key safety and endpoint data will be performed at regular intervals during the course of the trial. The primary objectives of these analyses will be to evaluate the accumulated data for high frequency of negative clinical outcomes in either of the two randomized arms. In addition, the interim monitoring will also involve a review of the control arm event rates, patient recruitment, compliance with the study protocol, status of data collection, and other factors that reflect the overall progress and integrity of the study. The results of the interim analyses and status reports will be carefully and confidentially reviewed by an NHLBI-appointed DSMB.

It is anticipated that the DSMB will meet every 6-months to review the accumulating data. Prior to each meeting, the DCC will conduct any requested statistical analyses and prepare a summary report along with the following information: patient enrollment reports, rates of compliance with the assigned testing strategy, frequency of protocol violations, and description of SAEs (statistical comparisons of the randomized arms with respect to these SAEs will use chi-square or other appropriate 2-sample methods). The extracted data files and analysis programs for each DSMB report will be archived and maintained at the DCC for the life of the study.

For futility monitoring, we will apply the inefficacy monitoring rule of Freidlin, Korn, and Gray⁵³ to stop the trial if the biomarker-guided strategy is not beneficial. We propose to use the conservative boundary LIBO along with a harm look at 25% of expected information. This approach will include 7 interim looks scheduled at roughly 25%, 40%, 50%, 60%, 70%, 80%, and 90%. With the proposed design, a total of 566

events are expected and the first interim review for futility and efficacy would be scheduled to occur after approximately 140 primary endpoint events have been observed. If the data suggested a benefit for the usual care arm with a p-value of <0.05, the Freidlin, Korn, and Gray approach would suggest stopping the trial at the 25% look. The second interim review would be scheduled after approximately 226 primary endpoint events have been observed. For the interim reviews at 40%, 50%, 60%, 70%, 80%, and 90%, the LIBO conservative boundary would suggest stopping the trial for inefficacy if the biomarker-guided arm had a hazard ratio > 1.0 compared to usual-care arm. The Freidlin, Korn, and Gray approach will result in a trivial loss of power and requires no sample size adjustment. The DSMB will weigh any trade-offs between short-term versus long-term results. We propose to use the method of Haybittle and Peto as a guide in interpreting interim efficacy analyses.^{54,55} This procedure requires large critical values (Z=3, p≤0.001) for every assessment until the planned final analysis. Because of the conservatism throughout the trial, the critical value at the final analysis is conducted at the "nominal" critical value.

The DSMB will weigh any trade-offs between short-term versus long-term results. The DSMB will play a valuable role in advising the study leadership on the relevance of advances in the diagnosis and treatment of patients with systolic HF. The DSMB would be asked to offer proper perspective on any therapeutic or diagnostic testing advances that may occur during the course of the trial. If protocol modifications are warranted, close consultation among the DSMB, the NHLBI staff and the study leadership will be required. A separate DSMB charter will outline the operating guidelines for the committee, and the protocol for evaluation of data—the charter will be created prior to patient randomization and agreed upon during the initial meeting of the DSMB. Minutes of all DSMB meetings will be prepared and distributed to committee members.

9. DATA MANAGEMENT PROCEDURES

9.1 Electronic Data Capture (EDC) System

To ensure an efficient and timely data capture system, a rapid transmission and integration of this information into the trial processes and study database, and the elimination of paper documents, the webbased electronic data capture system, known as InForm will be used.

9.2 Electronic Case Report Form (eCRF)

The eCRF for GUIDE-IT will have several forms including enrollment and demographics, relevant history, HF symptoms, physical exam results, laboratory results, baseline biomarker levels, and other baseline presenting characteristics; follow-up worksheets for use during regular follow-up visits and to track the patient's clinical course over time; and event worksheets for recording the circumstances and details surrounding the occurrence of a death or hospitalization. Economics and Quality of Life (EQOL) data will be collected as summarized above and detailed in the Manual of Operations. A dictionary, glossary of terms and instructions for completing the forms will be provided to the sites.

9.3 Data Management Process

We will use InForm software (described above) for data entry, screen handling and simple reports. We will use an Oracle database server on an existing UNIX-based network server for this operational database management. Data will be entered into the InForm eCRF by clinical site personnel. Any out-of-range values and missing key variables will be flagged and addressed, or answered at the site during the data entry process, allowing many queries to be resolved in real-time. Queries can also be generated from manual review of the data forms. These will be entered into the database and tracked in the same manner as the computer-generated queries.

We will compare distributions of selected variables across sites to ensure that consistent definitions are used. Examples of these variables include the following: frequency of missing critical variables, biological or medical history parameters, fields that define study procedure compliance and safety irregularities. In our surveillance, we will use statistical process control to ensure that issues not likely to be the result of normal random variation are investigated. The DCRI will create reports to identify trends in the data that may require additional clarification and training. These reports will be available to the sites and to the study leadership, as we work with the sites to correct negative trends and eliminate future data errors.

The DCRI will perform internal database quality-control checks and data audits during the trial and at the conclusion to track the frequency of random errors and to identify any systematic deviation requiring correction. Patients whose data are audited will be randomly selected from the total enrollment. Data management operations are also reviewed internally for their compliance with standard procedures, rules and guidelines for processing, quality control and productivity.

9.4 Data Quality Control

Data quality control goes beyond the data management process. All groups at the DCRI will work in tandem to ensure that the data collected in this study are as complete and correct as possible. A 4-step, multi-functional approach to data quality control will be implemented and is summarized below:

- Training: Prior to the start of enrollment, the physician investigators and study coordinators at each site will be trained with the clinical protocol and data collection procedures, including how to use the InForm system and complete the eCRF data. Initial investigator and coordinator training will occur with an InForm trainer and hands-on database interaction. This trainer will present slides, demonstrate key InForm functionality and guide attendees through practice exercises. Follow-up training and training for new study personnel will be conducted by DCRI personnel who will present slides, demonstrate the system and guide attendees through practice exercises using on-line web-based teleconferences.
- 2. Monitoring: The clinical and data coordinating center will ensure that data collection is being handled properly, will provide in-service training, and address questions from site investigators and coordinators. Data quality and completeness will be reviewed by the DCRI team on a regular and ongoing basis, and any issues noted will be addressed with the site. Monitoring visits will be completed as described in the Clinical Monitoring Plan.
- 3. Managing data: After the data have been transferred to SAS for statistical summarization, data description, and data analysis, further cross-checking of the data will be performed with discrepant observations being flagged and appropriately resolved through a data query system.
- 4. Reviewing data: Deaths and hospitalization events will be reviewed by the CEC to ensure an appropriate standardized classification of the component events comprising the primary composite endpoint. The DCC will provide the CEC with detailed information for classification and adjudication of these events. The CEC will be blinded to the randomized treatment strategy assignment to ensure unbiased evaluation of outcome events.

